11.1.3 Methods for Evaluation of MRD

The high relapse rate seen in adult ALL indicates the lack of eradication of MRD despite morphologic remission. Several techniques, including monitoring of fusion gene transcripts; clonal immunoglobulin heavy chain gene rearrangement; or multicolor flow cytometry have shown reliability in estimating the risk of relapse in ALL patients.¹⁰⁰

Given the equivalence of PCR techniques and flow cytometry in monitoring MRD in ALL patients,¹⁰¹ a flow cytometric approach will be used for MRD assessment in this study. This approach has been adopted for all patients with ALL in our institution and for patients with NHL involving the bone marrow. Furthermore, the flow cytometry laboratory at Johns Hopkins is a reference laboratory for MRD monitoring in ALL for all COG studies. Those patients with unique gene fusions detectable by PCR will also be monitored for MRD by specific PCR tests following the completion of blinatumomab treatment, and then per the institutional standard-of-care. Collected samples may also be used for the assessment of MRD at a molecular level by high-throughput sequencing of IGH as previously described,¹⁰² or by PCR for patients with a known fusion gene transcript.

11.1.4 Response Criteria

Responses will be assessed at the conclusion of cycles 1 and 2 and in follow-up given the response definitions provided above.

11.1.5 Duration of Response

Duration of overall response: The duration of overall response is measured from the time criteria are met for CR or CRi (whichever is first recorded) until the first date that relapsed disease is objectively documented.

11.1.6 Progression-Free Survival

Progression-free survival (PFS) is defined as the duration of time from start of treatment to time of progression or death, whichever occurs first.

12. STUDY OVERSIGHT AND DATA REPORTING / REGULATORY REQUIREMENTS

Adverse event lists, guidelines, and instructions for AE reporting can be found in Section 7.0 (Adverse Events: List and Reporting Requirements).

12.1 Study Oversight

This protocol is monitored at several levels, as described in this section. The Protocol Principal Investigator is responsible for monitoring the conduct and progress of the clinical trial, including the ongoing review of accrual, patient-specific clinical and laboratory data, and routine and serious adverse events; reporting of expedited adverse events; and accumulation of reported adverse events from other trials testing the same drug(s). The Protocol Principal Investigator and statistician have access to the data at all times through the CTMS web-based reporting portal.

For the Phase 1 portion of this study, all decisions regarding dose escalation/expansion/de-escalation require sign-off by the Protocol Principal Investigator through the CTMS/IWRS. In addition, for the Phase 1 portion, the Protocol Principal Investigator will have at least monthly, or more frequently, conference calls with the Study Investigators and the CTEP Medical Officer(s) to review accrual, progress, and adverse events and unanticipated problems.

All Study Investigators at participating sites who register/enroll patients on a given protocol are responsible for timely submission of data via Medidata Rave and timely reporting of adverse events for that particular study. This includes timely review of data collected on the electronic CRFs submitted via Medidata Rave.

All studies are also reviewed in accordance with the enrolling institution's data safety monitoring plan.

12.2 Data Reporting

Data collection for this study will be done exclusively through Medidata Rave. Access to the trial in Rave is granted through the iMedidata application to all persons with the appropriate roles assigned in the Regulatory Support System (RSS). To access Rave via iMedidata, the site user must have an active CTEP IAM account (check at < <https://ctepcore.nci.nih.gov/iam> >) and the appropriate Rave role (Rave CRA, Read-Only, CRA (Lab Admin, SLA, or Site Investigator) on either the LPO or participating organization roster at the enrolling site. To hold Rave CRA role or CRA Lab Admin role, the user must hold a minimum of an AP registration type. To hold the Rave Site Investigator role, the individual must be registered as an NPIVR or IVR. Associates can hold read-only roles in Rave.

Upon initial site registration approval for the study in RSS, all persons with Rave roles assigned on the appropriate roster will be sent a study invitation e-mail from iMedidata. To accept the invitation, site users must log into the Select Login (<https://login.imedidata.com/selectlogin>) using their CTEP-IAM user name and password, and click on the "accept" link in the upper right-corner of the iMedidata page. Please note, site users will not be able to access the study in

Rave until all required Medidata and study specific trainings are completed. Trainings will be in the form of electronic learnings (eLearnings), and can be accessed by clicking on the link in the upper right pane of the iMedidata screen.

Users that have not previously activated their iMedidata/Rave account at the time of initial site registration approval for the study in RSS will also receive a separate invitation from iMedidata to activate their account. Account activation instructions are located on the CTSU website, Rave tab under the Rave resource materials (Medidata Account Activation and Study Invitation Acceptance). Additional information on iMedidata/Rave is available on the CTSU members' website under the Rave tab or by contacting the CTSU Help Desk at [name] or by e-mail at [contact].

12.2.1 Method

This study will be monitored by the Clinical Trials Monitoring Service (CTMS). Data will be submitted to CTMS at least once every two weeks via Medidata Rave (or other modality if approved by CTEP). Information on CTMS reporting is available at <http://www.theradex.com/clinicalTechnologies/?National-Cancer-Institute-NCI-11>. On-site audits will be conducted three times annually (one annual site visit and two data audits). For CTMS monitored studies, after users have activated their accounts, please contact the Theradex Help Desk at [contact] or by email at [contact] for additional support with Rave and completion of CRFs.

12.2.2 Responsibility for Data Submission

For ETCTN trials, it is the responsibility of the PI(s) at the site to ensure that all investigators at the ETCTN Sites understand the procedures for data submission for each ETCTN protocol and that protocol specified data are submitted accurately and in a timely manner to the CTMS via the electronic data capture system, Medidata Rave.

Data are to be submitted via Medidata Rave to CTMS on a real-time basis, but no less than once every 2 weeks. The timeliness of data submissions and timeliness in resolving data queries will be tracked by CTMS. Metrics for timeliness will be followed and assessed on a quarterly basis. For the purpose of Institutional Performance Monitoring, data will be considered delinquent if it is greater than 4 weeks past due.

Data from Medidata Rave and CTEP-AERS is reviewed by the CTMS on an ongoing basis as data is received. Queries will be issued by CTMS directly within Rave. The queries will appear on the Task Summary Tab within Rave for the CRA at the ETCTN to resolve. Monthly web-based reports are posted for review by the Drug Monitors in the IDB, CTEP. Onsite audits will be conducted by the CTMS to ensure compliance with regulatory requirements, GCP, and NCI policies and procedures with the overarching goal of ensuring the integrity of data generated from NCI-sponsored clinical trials, as described in the ETCTN Program Guidelines, which may be found on the CTEP (http://ctep.cancer.gov/protocolDevelopment/electronic_applications/adverse_events.htm) and CTSU websites.

An End of Study CRF is to be completed by the PI, and is to include a summary of study endpoints not otherwise captured in the database, such as (for phase 1 trials) the recommended phase 2 dose (RP2D), and a description of any dose-limiting toxicities (DLTs). CTMS will utilize a core set of eCRFs that are Cancer Data Standards Registry and Repository (caDSR) compliant (<http://cbiit.nci.nih.gov/ncip/biomedical-informatics-resources/interoperability-and-semantics/metadata-and-models>). Customized eCRFs will be included when appropriate to meet unique study requirements. The PI is encouraged to review the eCRFs, working closely with CTMS to ensure prospectively that all required items are appropriately captured in the eCRFs prior to study activation. CTMS will prepare the eCRFs with built-in edit checks to the extent possible to promote data integrity.

CDUS data submissions for ETCTN trials activated after March 1, 2014, will be carried out by the CTMS contractor, Theradex. CDUS submissions are performed by Theradex on a monthly basis. The trial's lead institution is responsible for timely submission to CTMS via Rave, as above.

Further information on data submission procedures can be found in the ETCTN Program Guidelines (http://ctep.cancer.gov/protocolDevelopment/electronic_applications/adverse_events.htm).

12.3 CTEP Multicenter Guidelines

N/A

12.4 Collaborative Agreements Language

The agent(s) supplied by CTEP, DCTD, NCI used in this protocol is/are provided to the NCI under a Collaborative Agreement (CRADA, CTA, CSA) between the Pharmaceutical Company(ies) (hereinafter referred to as "Collaborator(s)") and the NCI Division of Cancer Treatment and Diagnosis. Therefore, the following obligations/guidelines, in addition to the provisions in the "Intellectual Property Option to Collaborator" (http://ctep.cancer.gov/industryCollaborations2/intellectual_property.htm) contained within the terms of award, apply to the use of the Agent(s) in this study:

1. Agent(s) may not be used for any purpose outside the scope of this protocol, nor can Agent(s) be transferred or licensed to any party not participating in the clinical study. Collaborator(s) data for Agent(s) are confidential and proprietary to Collaborator(s) and shall be maintained as such by the investigators. The protocol documents for studies utilizing Agents contain confidential information and should not be shared or distributed without the permission of the NCI. If a copy of this protocol is requested by a patient or patient's family member participating on the study, the individual should sign a confidentiality agreement. A suitable model agreement can be downloaded from: <http://ctep.cancer.gov>.
2. For a clinical protocol where there is an investigational Agent used in combination with (an)other Agent(s), each the subject of different Collaborative Agreements, the access to and use of data by each Collaborator shall be as follows (data pertaining to such combination use

shall hereinafter be referred to as "Multi-Party Data”):

- a. NCI will provide all Collaborators with prior written notice regarding the existence and nature of any agreements governing their collaboration with NCI, the design of the proposed combination protocol, and the existence of any obligations that would tend to restrict NCI's participation in the proposed combination protocol.
 - b. Each Collaborator shall agree to permit use of the Multi-Party Data from the clinical trial by any other Collaborator solely to the extent necessary to allow said other Collaborator to develop, obtain regulatory approval or commercialize its own Agent.
 - c. Any Collaborator having the right to use the Multi-Party Data from these trials must agree in writing prior to the commencement of the trials that it will use the Multi-Party Data solely for development, regulatory approval, and commercialization of its own Agent.
3. Clinical Trial Data and Results and Raw Data developed under a Collaborative Agreement will be made available to Collaborator(s), the NCI, and the FDA, as appropriate and unless additional disclosure is required by law or court order as described in the IP Option to Collaborator (http://ctep.cancer.gov/industryCollaborations2/intellectual_property.htm). Additionally, all Clinical Data and Results and Raw Data will be collected, used and disclosed consistent with all applicable federal statutes and regulations for the protection of human subjects, including, if applicable, the *Standards for Privacy of Individually Identifiable Health Information* set forth in 45 C.F.R. Part 164.
 4. When a Collaborator wishes to initiate a data request, the request should first be sent to the NCI, who will then notify the appropriate investigators (Group Chair for Cooperative Group studies, or PI for other studies) of Collaborator's wish to contact them.
 5. Any data provided to Collaborator(s) for Phase 3 studies must be in accordance with the guidelines and policies of the responsible Data Monitoring Committee (DMC), if there is a DMC for this clinical trial.
 6. Any manuscripts reporting the results of this clinical trial must be provided to CTEP by the Group office for Cooperative Group studies or by the principal investigator for non-Cooperative Group studies for immediate delivery to Collaborator(s) for advisory review and comment prior to submission for publication. Collaborator(s) will have 30 days from the date of receipt for review. Collaborator shall have the right to request that publication be delayed for up to an additional 30 days in order to ensure that Collaborator's confidential and proprietary data, in addition to Collaborator(s)'s intellectual property rights, are protected. Copies of abstracts must be provided to CTEP for forwarding to Collaborator(s) for courtesy review as soon as possible and preferably at least three (3) days prior to submission, but in any case, prior to presentation at the meeting or publication in the proceedings. Press releases and other media presentations must also be forwarded to CTEP prior to release. Copies of any manuscript, abstract and/or press release/ media presentation should be sent to:
Email: [contact]

NCI Protocol #: 10030
Version Date: January 3, 2023

The Regulatory Affairs Branch will then distribute them to Collaborator(s). No publication, manuscript or other form of public disclosure shall contain any of Collaborator's confidential/proprietary information.

13. STATISTICAL CONSIDERATIONS

13.1 Overall

This is a multi-site, open-label, Phase 1 study of evaluating safety, tolerability, and preliminary antitumor activity of blinatumomab and nivolumab with or without ipilimumab in patients with CD19+ Pre-B ALL and CD19+ MPAL. The study consists of two parts: dose escalation for blinatumomab and nivolumab with and without ipilimumab and dose expansion at MTD. The dose expansion cohort will only be initiated once the MTD for the combination therapy has been established. In each part of the study, a ten-day run-in of blinatumomab prior to combination therapy will be incorporated to help determine the effect of blinatumomab on immune-related parameters of each patient's leukemia.

13.2 Analysis Population

- Safety Analysis Set: All subjects who receive at least one dose of study drug.
- Dose-Limiting Toxicity Evaluation Set: A subject must meet one of the following 3 criteria to be evaluable for dose-escalation decisions: receive all of the scheduled doses of combination therapy and has completed 6 weeks of treatment without a DLT; experience a DLT in the first 6 weeks of combination therapy; or withdrawn from the study prior to completing 6 weeks of combination treatment due to a DLT.
- Efficacy Evaluable Analysis Set: All subjects who receive at least one dose of study drug, have an adequate baseline disease assessment and at least one post-baseline response assessment.

13.3 Study Design/Endpoints

13.3.1 Primary Objectives

- 13.3.1.1 Adverse events and toxicities will be tabulated and reported by type and grade for all dose levels of all treatment combinations and the proportions reported with exact 95% binomial confidence intervals.
- 13.3.1.2 The maximum tolerated dose (MTD) of the combination of blinatumomab plus nivolumab, and blinatumomab plus both nivolumab and ipilimumab will be determined in subjects with poor-risk, relapsed or refractory CD19⁺ Pre-B cell ALL or CD19⁺ mixed phenotype acute leukemia (MPAL).

13.3.2 Secondary Objectives

- 13.3.2.1 The frequency distribution of responses, including CR, CRi or progressive disease (PD) by treatment arm and dose level for all patients on study will be determined and reported with exact 95% confidence intervals.

- 13.3.2.2 For patients who have a clinical response, the frequency of MRD+ vs. MRD-responses will be reported by treatment arm and dose level for all patients on study.
- 13.3.2.3 For patients who have a clinical response, duration of response (DOR) will be analyzed as a time-to-event outcome with the duration being measured as the time from measured response to progressive disease, death, or study end.
- 13.3.2.4 Overall survival will be measured from the first day of treatment on the study until death or last known follow up.

13.3.3 Exploratory Objectives

- 13.3.3.1 The absolute lymphocyte count and the distribution of T cell subsets (CD4⁺, CD8⁺, T_{regs}, T_{effs}) and their differentiation status, NK cells, and B cells before and post-blinatumomab, and immune checkpoint inhibitor(s) therapy in both peripheral blood and the bone marrow microenvironment will be determined.
- 13.3.3.2 Changes in T cell co-signaling receptors expression in defined T cell subpopulations and their canonic transcription factor expression in both peripheral blood and bone marrow before and post-blinatumomab, and immune checkpoint inhibitor(s) therapy will be recorded.
- 13.3.3.3 Changes in expression of co-signaling molecules on leukemia blasts (CD10⁺/CD19⁺/CD34⁺) before and after treatment with blinatumomab and checkpoint inhibitors will be examined.
- 13.3.3.4 Serum levels of cytokines before and after treatment with blinatumomab and checkpoint inhibitors, including the levels of sCTLA-4, will be determined.
- 13.3.3.5 Immune profiling of T cell repertoire and characterization of T cell transcriptional signature before and after treatment will be determined.

13.4 Study Design

This study proposal will be a phase 1 trial of blinatumomab plus immune checkpoint inhibition in patients with relapsed/refractory ALL or those with a new diagnosis of ALL who cannot receive standard induction. The first part of the study will be a dose escalation following a 3+3 design for the combination of blinatumomab plus nivolumab. The study will start with the recommended dose of blinatumomab in relapsed/refractory ALL. Nivolumab will be started at the recommended doses for monotherapy for metastatic melanoma. This design is being used as an added safety measure and a more controlled start of the study to minimize the risk of unexpected toxicities or other issues that may occur in the combination treatment of blinatumomab with either ipilimumab or nivolumab.

The first three patients will be enrolled at dose level DL A1 and monitored for the first cycle of treatment (42 days) for DLTs before enrolling additional patients. If less than 2 patients

experience a DLT, an additional 3 patients will be enrolled at that dose level. If 0 or 1 out of 6 patients have a DLT, that dose level will be deemed safe. If 2 or 3 of the first 3 patients experience a DLT, that study arm may de-escalate to dose level DL A-1 (only after CTEP approval) and another 3 patients will be enrolled. If less than 2 patients experience a DLT in the de-escalated dose, an additional 3 patients will be enrolled at that dose. If 0 or 1 out of 6 patients have a DLT, the de-escalated dose will be deemed safe. If 2 or 3 patients experience a DLT, that study arm will be stopped for review.

When the safety of blinatumomab in combination with nivolumab is confirmed, the study will expand to treat patients with this combination plus ipilimumab. A standard 3+3 design will be used to assess the safety and tolerability of the combination. Two dose levels (DL B1, DL B-1,) are available. If DL A1 was deemed safe, then three patients will be enrolled at DL B1. If ≤ 1 of 3 patients experience a DLT during the first cycle of treatment (42 days), at DL B1, an additional 3 patients will be enrolled at DL B1. If no more than 1 of 6 patients experience a DLT, then it will be defined as the MTD. If 2 or more of 3 or 6 patients experience a DLT at DL B1, then dose de-escalation may be implemented BUT ONLY after CTEP approval and the next three patients may be enrolled at DL B-1. If ≤ 1 of 3 patients experience a DLT during the first cycle of treatment (42 days), an additional three patients will be enrolled at DL B-1. If 2 or more of 3 or 6 patients experience a DLT at DL B-1, then dose escalation will be halted and the combination of blinatumomab, nivolumab and ipilimumab will not be further pursued in this patient population unless additional data become available supporting different doses or schedules of nivolumab and ipilimumab administration. This will require review of all toxicity, discussion with CTEP and official study amendment.

When the MTD of blinatumomab in combination with ipilimumab and nivolumab is determined, an additional 6 patients will be enrolled in an expansion cohort to further characterize safety, tolerability and any preliminary signs of biological or clinical activity of the triplet blinatumomab/nivolumab plus ipilimumab. An expansion cohort of 6 subjects will be also pursued at MTD for doublet of blinatumomab and nivolumab only to further characterize safety, tolerability and any preliminary signs of biological or clinical activity in this cohort.

13.4.1 Dose Expansion

Continuous monitoring of safety will be completed during the enrollment and treatment period of each expansion cohort. If it becomes evident that the proportion of patients experiencing a treatment-related toxicity meeting DLT criteria convincingly exceeds 30%, the study will be halted for a safety consultation. The toxicity stopping rule will hold enrollment if the posterior probability of failure being larger than 0.30 is 70% or higher. The prior for this monitoring rule is beta (1,2). This means that our prior guess at the proportion of failures is 33%, and there is 90% probability that this proportion is between 2.5% and 77.6%. The monitoring rule and operating characteristics are given below.

- Stop if 2 out of 2 patients experience a DLT: $\Pr(\text{Risk} > 0.3 \mid \text{Data}) = 0.916$
- Stop if 2 out of 3 patients experience a DLT: $\Pr(\text{Risk} > 0.3 \mid \text{Data}) = 0.837$
- Stop if 2 out of 4 patients experience a DLT: $\Pr(\text{Risk} > 0.3 \mid \text{Data}) = 0.744$
- Stop if 3 out of 5 patients experience a DLT: $\Pr(\text{Risk} > 0.3 \mid \text{Data}) = 0.874$
- Stop if 3 out of 6 patients experience a DLT: $\Pr(\text{Risk} > 0.3 \mid \text{Data}) = 0.806$

Operating Characteristics of stopping rule for toxicity, based on 5000 simulations:

True Toxicity Rate	Probability of declaring treatment too toxic	Average sample size
20%	17%	3.9
25%	26.8%	3.8
30%	34.6%	3.7
35%	43.1%	3.6
40%	52.7%	3.5
45%	61%	3.4
50%	68.8%	3.2

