5.2.2 Dose Expansion

An additional 6 patients will be treated at the MTD for both combinations: blinatumomab and nivolumab alone; and blinatumomab/nivolumab plus ipilimumab to gain additional safety information and to explore preliminary biological and clinical activity of these combination therapies. When the MTD of blinatumomab in combination with nivolumab and ipilimumab is determined (either DLB1: Nivolumab 240 mg plus Ipilimumab 1 mg/kg or DLB-1: Nivolumab 80 mg and Ipilimumab 1 mg/kg), an additional 6 patients will be enrolled in an expansion cohort to further characterize safety, tolerability and any preliminary signs of biological or clinical activity of nivolumab and ipilimumab in combination with blinatumomab. However, if the combination of blinatumomab, nivolumab and ipilimumab is found to be intolerable, then the expansion cohort of an additional 6 patients will be only pursued at the MTD of blinatumomab and nivolumab alone (either DLA1: Nivolumab 240 mg or DLA-1: Nivolumab 80 mg) to further characterize safety, tolerability and any preliminary signs of biological or clinical activity for blinatumomab and nivolumab combination.

Based on the review of safety and efficacy data, in discussion with CTEP on 03/13/2019, a separate expansion cohort of an additional 6 patients at the MTD of blinatumomab and nivolumab alone was added to the study in addition to the expansion cohort of nivolumab, ipilimumab and blinatumomab (triple combination) to further characterize safety, tolerability and

any preliminary signs of biological or clinical activity for this combination.

Continuous evaluation of adverse events will be performed throughout enrollment in the expansion cohort. If, at any time, the aggregate rate of treatment-related toxicities meeting DLT criteria exceeds 30% across all subjects treated in the expansion cohort, the safety data will be discussed and further enrollment may be suspended.

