13.4.2 Early Stopping for Safety in the Post-Transplant Setting

Because many patients enrolled in this protocol will be candidates for a subsequent allo-HSCT, and there have been recent reports of increased toxicity among patients who undergo allo-HSCT following treatment with PD-1 inhibitors, all patients who go onto allo-HSCT following the completion of the clinical protocol will undergo continuous monitoring. The clinical failures of acute grade 3-4 graft versus host disease and post-transplant non-relapse mortality will be monitored continuously for the first 100 post-transplant days. If it becomes evident that the proportion of acute grade 3-4 graft versus host disease is greater than 25% or the proportion of non-relapse mortality is greater than 20% then the study would be held for a safety consultation.

Acute Grade 3-4 GVHD

The acute GVHD grade 3-4 stopping rule will hold enrollment if the posterior probability of failure being larger than 0.25 is 70% or higher. The prior for this monitoring rule is beta(1,3). This means that our prior guess at the proportion of failures is 25%, and there is 90% probability that this proportion is between 1.7% and 63.2%. The following table shows the resulting rules.

Safety review triggered if number of patients with grade 3-4 GVHD is:	2	3	4	5	6	7	8	9	10	11
Number of patients is between:	2-4	5-8	9-11	12-15	16-18	19-22	23-26	27-30	31-33	34-36

For example, the rule will call for a safety review if 3 out of the first 5 patients experience acute grade 3-4 GVHD. The table below shows the percent of times the stopping rule will halt the study for a safety review and the average sample size under different hypothetical risks of grade 3-4 acute GVHD.

Operating Characteristics of stopping rule for GVHD, based on 5000 simulations:

True acute or chronic GVHD grade 3-4 rate	Probability of stopping for excess GVHD grade 3-4	Average Sample Size
10%	8.0%	31.7
15%	20.7%	28.4
20%	37.1%	24.6
25%	58.5%	19.4
30%	77.3%	14.9
35%	89.2%	11.3
40%	95.9%	8.4

Non-Relapse Mortality

The non-relapse mortality safety stopping rule will hold enrollment if the posterior probability of failure being larger than 0.20 is 70% or higher. The prior for this monitoring rule is beta(1,4). This means that our prior guess at the proportion of failures is 20%, and there is 90% probability that this proportion is between 0.60% and 60.2%. The following table shows the resulting rules.

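### The operating-characteristics table for the expansion-cohort toxicity rule (Section 13.4.1) does not belong to a 6-patient cohort: six of seven average sample sizes are impossible and all seven stopping probabilities are too low

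*Combined protocol and SAP*

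**What the plan says.** Section 13.4 plans two expansion cohorts of 6. For the triplet, "an additional 6 patients will be enrolled in an expansion cohort to further characterize safety"; for the doublet, "An expansion cohort of 6 subjects will be also pursued at MTD for doublet of blinatumomab and nivolumab only". Section 13.4.1 monitors the cohorts separately: "Continuous monitoring of safety will be completed during the enrollment and treatment period of each expansion cohort". The criterion, with a Beta(1,2) prior, is: "The toxicity stopping rule will hold enrollment if the posterior probability of failure being larger than 0.30 is 70% or higher". Five boundaries follow: 2 of 2, 2 of 3, 2 of 4, 3 of 5, and finally "Stop if 3 out of 6 patients experience a DLT". Below them is a table headed "Operating Characteristics of stopping rule for toxicity, based on 5000 simulations", giving a stopping probability and an average sample size for true rates of 20% to 50%. No maximum sample size is stated for the simulation.

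Section 5.2.2 also describes monitoring of the expansion. There the trigger is an aggregate rate above 30%, after which "the safety data will be discussed and further enrollment may be suspended".

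**The concern.** A rule that cannot stop before patient 2, in a cohort of 6, cannot average 3.9 patients when it stops only 17% of the time, because the other 83% of cohorts run to 6. The table therefore seems to come from a different design than the one written above it.

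This table is the plan's only evidence of how often the expansion safety rule fires and how many patients are treated before it does. Anyone judging whether the rule is too loose or too strict would be working from the wrong figures.

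**Working it through.** **Inputs.** From Section 13.4.1: prior Beta(1,2); criterion Pr(risk > 0.30) ≥ 0.70; boundaries 2/2, 2/3, 2/4, 3/5, 3/6; 5000 simulations. From Sections 13.4 and 5.2.2: maximum n = 6.

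**Step 1: the rule itself.** With x events in n patients the posterior is Beta(1+x, 2+n−x). Pr(risk > 0.30) is 0.916, 0.837, 0.744, 0.874 and 0.806 at the five boundaries, as printed. The prior 90% interval of 2.5% to 77.6% also reproduces.

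**Step 2: a bound from the table's own figures.** Stopped cohorts have at least 2 patients and the rest have 6, so average n ≥ 2P + 6(1−P) = 6 − 4P.

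| True rate | Printed P | Minimum 6 − 4P | Printed average n |
|---|---|---|---|
| 20% | 17% | 5.32 | 3.9 |
| 25% | 26.8% | 4.93 | 3.8 |
| 30% | 34.6% | 4.62 | 3.7 |
| 35% | 43.1% | 4.28 | 3.6 |
| 40% | 52.7% | 3.89 | 3.5 |
| 45% | 61% | 3.56 | 3.4 |
| 50% | 68.8% | 3.25 | 3.2 |

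The first six rows are impossible even allowing for rounding. The seventh (3.248 before rounding) is not excluded by the bound alone, but it would need every stop to occur at patient 2.

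**Step 3: exact values at 6 patients.** Let p be the true rate and q = 1 − p. A stop by patient 4 means at least 2 events in 4: 1 − q⁴ − 4pq³. A cohort that continues has at most 1 event, so 3 of 5 cannot be newly reached. A stop at 3 of 6 needs exactly 1 event in the first 4 and events in both of the last two: 4pq³ × p². Hence

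P(stop) = 1 − q⁴ − 4pq³ + 4p³q³.

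Stops at patients 2, 3 and 4 have probabilities p², 2p²q and 3p²q², and every other cohort uses 6 patients. So

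average n = 6 − 4p² − 6p²q − 6p²q².

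At p = 0.30: P = 1 − 0.2401 − 0.4116 + 0.0370 = 0.385, and average n = 6 − 0.36 − 0.378 − 0.2646 = 5.00.

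| True rate | P: exact / printed | Gap in simulation SEs | Average n: exact / printed |
|---|---|---|---|
| 20% | 19.7% / 17% | 4.8 | 5.49 / 3.9 |
| 25% | 28.8% / 26.8% | 3.1 | 5.26 / 3.8 |
| 30% | 38.5% / 34.6% | 5.7 | 5.00 / 3.7 |
| 35% | 48.4% / 43.1% | 7.5 | 4.72 / 3.6 |
| 40% | 58.0% / 52.7% | 7.6 | 4.44 / 3.5 |
| 45% | 67.0% / 61% | 9.0 | 4.15 / 3.4 |
| 50% | 75.0% / 68.8% | 10.1 | 3.88 / 3.2 |

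The simulation SE is √(P(1−P)/5000), for example √(0.385 × 0.615/5000) = 0.7 points at a true 30%.

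**Step 4: likely source.** Capping the same boundaries at 4 patients gives P of 18.1, 26.2, 34.8, 43.7, 52.5, 60.9 and 68.8%, and average n of 3.86, 3.78, 3.69, 3.60, 3.49, 3.37 and 3.25. Every printed stopping probability is within 2.0 SE of these, and every average within 0.05 patients. A cap of 5 gives the same stopping probabilities but averages of 4.68 down to 3.56, so the average-n column is what points to 4.

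The tables in Section 13.4.2 show the same two-patient shortfall. The one headed "Operating Characteristics of stopping rule for GVHD, based on 5000 simulations" lists boundaries to 36 patients and prints an average of 31.7 at a 10% rate; a maximum of 36 gives 33.6 and 34 gives 31.8. For non-relapse mortality at 10% the printed average is 30.5; 36 gives 32.4 and 34 gives 30.6 (taking the unlisted n = 33 as boundary 9).

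**Step 5: two loose ends in the rule.** One event in the first patient has posterior 0.784, which meets the 70% criterion, yet the list begins at 2 patients. And 2 of 6 is an observed 33%, above the Section 5.2.2 trigger, but its posterior is 0.552, below the Section 13.4.1 criterion.

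**The case against.** **The stopping column depends on one boundary.** The whole gap in stopping probability comes from 3 of 6 (1.6, 3.7 and 6.3 points at true rates of 20%, 30% and 50%). By then the cohort is full and no enrollment is left to hold. Without that boundary the printed probabilities agree with exact values within 2 SE. This is a fair reading of that column, but 3 of 6 is a listed stop and the column header concerns a verdict of excess toxicity, so counting it is the natural reading. The average-n column fails either way.

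**The bound assumes no stop at 1 of 1.** If such a stop applied, the bound would be 6 − 5P and would exclude only four rows. That is correct, but the printed list starts at 2, as do both rules in Section 13.4.2. A stop at 1 of 1 would also move the exact stopping probabilities further from print, to 29.5% at a true 20% and 47.9% at 30%.

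**Escalation patients might count.** Section 13.5 speaks of 9 or 12 patients at the expanded dose level. Including them would lengthen the monitored sequence, whereas the printed averages are too short.

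**Real enrollment may overlap.** The DLT window is 42 days and no staggering is stated for the expansion, so more patients could be treated than the exact averages suggest. This stands as a limit on the corrected figures.

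**The practical effect is modest.** No boundary changes, and at high toxicity the rule fires more often than stated. This also stands, and it limits the seriousness of the point.

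**Conclusion.** The concern holds. For a 6-patient cohort under the listed boundaries, the table understates the chance of stopping by 2.0 to 3.9 points at true rates of 20% to 30%, and by 5.3 to 6.2 points at 35% to 50%. It understates the average number treated by 0.7 to 1.6 patients. Simulation error does not explain gaps of 3.1 to 10.1 standard errors.

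The result assumes the list as printed (first stop at 2 of 2, with 3 of 6 counted as a stop), independent patients with a common event rate, and each patient's outcome known before the next enrolls. The 4-patient cap is an inference about the cause, and the error does not depend on it. The rule's boundaries and posteriors are right, so this corrects reported performance and leaves conduct unchanged. It should be fixed.

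**What to change.** - Replace the Section 13.4.1 table with the 6-patient values above, and state the maximum n and the assumption of sequential evaluation. Leave the five boundaries and posteriors as they are.
- State the first look. The printed list implies the second patient, consistent with Section 13.4.2. If the sponsor means the 70% criterion to apply at the first patient, both the list and the table must change.
- Reconcile Sections 5.2.2 and 13.4.1, saying whether they describe one rule or a review trigger plus a hold. That choice is the sponsor's.
- While rerunning, confirm the maximum n behind the two Section 13.4.2 tables.

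The cost is one replaced table, two clarifying sentences and a few minutes of calculation. The stated chance of a hold becomes slightly less favourable at the lower rates: 17% becomes 19.7% at a true 20%, and 34.6% becomes 38.5% at 30%.
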